#### Outcome Measures:

**Primary Outcomes:** The primary outcome will be inpatient and outpatient opioid use, defined as morphine milligram equivalents. Morphine milligram equivalent dose (MME) will be calculated to standardize across different medications. Pill counts will be conducted at follow-up visits to account for unused opioids, and patients will be provided with opioid disposal kits. Use of non-opioid pain medications (i.e. NSAIDS, acetaminophen, gabapentin) will be documented. Patients will also be asked about their use of nonpharmaceutical modalities at each follow-up visit or phone call, including cryotherapy, aromatherapy, and cognitive strategies.

**Secondary Outcomes:** The secondary outcomes will be patient-reported outcomes, measured by the PROMIS 29, which includes physical function, anxiety, depression, fatigue, sleep disturbance, ability to participate in social roles and activities, pain interference and pain intensity. In addition, pain scores from the inpatient stay and clinic visits will be abstracted from the medical record. PROMIS will be administered during the hospitalization and at follow-up visits or via phone calls, emails, or text messages at 2, 6, and 12 weeks. VAS pain scores will be abstracted from the medical record during the hospitalization and at each follow-up visit.

**Process Measures and Feasibility:** Process measures will be collected to document feasibility of implementing TENS postoperatively among this patient population, including: patient compliance with TENS after discharge, number of times each day TENS was used, duration of each TENS session, and average frequency/amplitude of electrical current for each patient.

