## Transcutaneous Electrical Nerve Stimulation (TENS) for Pain Alleviation in Perioperative Fracture Patients

### Specific Aims:

Opioid overdoses continue to increase, and the path to addiction often begins with a prescription. Half of postoperative patients receive an opioid prescription. Multimodal pain management, including cognitive, physical, and pharmaceutical strategies, reduces reliance on opioids alone. Transcutaneous nerve stimulation (TENS) is one physical strategy; this study aims to evaluate the effectiveness of TENS as part of postoperative pain management.

**Specific Aim 1:** To pilot the use of TENS among a postoperative lower extremity injury population as part of multimodal pain management.

$H_0$ : TENS cannot be delivered safely among this population.

$H_A$ : TENS can be delivered safely among this population.

**Specific Aim 2:** To compare utilization of inpatient and outpatient pain medications of patients treated with TENS and historical controls.

$H_0$ : Patients treated with TENS will require the same amount of opioids as historical controls.

$H_A$ : Patients treated with TENS will require less opioids (lower morphine milligram equivalent – MME) than historical controls during hospitalization and throughout 3-month follow up.

**Specific Aim 3:** To compare patient-reported outcomes of patients treated with TENS and historical controls.

$H_0$  1: Patients treated with TENS will experience equivalent patient-reported outcomes as compared to historical controls.

$H_A$  1: Patients treated with TENS will experience greater improvement in patient-reported outcomes (PROMIS 29) relative to baseline as compared to historical controls.

$H_0$  2: Patients treated with TENS will report higher pain scores as compared to historical controls.

$H_A$  2: Patients treated with TENS will report equivalent or lower pain scores as compared to historical controls.

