#### Treatment Groups:

The prospectively enrolled patients will have TENS pads placed immediately following surgery, prior to PACU. The TENS unit will be connected to the pads and turned on in the PACU. Each patient will receive instructions for suggested use of the device. They will be allowed to individualize the frequency/amplitude of the current to reach a "strong sub-noxious" stimulation, as recommended by previous studies. They will be asked to aim for 4x45 minute sessions each day. This protocol was previously published by a separate group demonstrating decreased post-operative pain levels with adjunctive TENS use.

This institution has an ongoing research study which collects injury characteristics, patient-reported outcomes, and kinematic/performance data for orthopaedic trauma patients with lower-extremity injuries. Patients with similar injuries as the prospectively enrolled patients will be identified in this database to serve as controls, because TENS units were not previously used at this institution for pain management. Our institution also has a database of all opioid prescriptions as well as risk factors that can be used to provide these data for the controls.

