#### Sample Size:

The sample size estimate was based on data from the meta-analysis conducted by Tedesco et al. This is a superiority prospective observational study with matched historical controls and the primary outcome variable is morphine milligram equivalents (MME) within the first 48 hours postoperatively. The assumed mean MME for the TENS group is 6.4 and 9.9 for the control group with a pooled standard deviation of 5.5. Using a two-sided independent T-test, .05 level of significance and 80% power, 40 patients per group is needed for a total study sample of 80 patients. Therefore, we will enroll 50 patients in order to account for loss to follow-up. Historical controls will be injury-matched from a prospectively collected, historical database on mobility (N=50).

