#### Study Procedures:

**Screening & Enrollment:** All patients 18 years or older presenting for initial treatment, nonunion or limb length deformity correction of the femur, tibia (plateau, shaft, pilon), or hindfoot/ankle will be screened for eligibility. Once eligibility has been confirmed, a research coordinator and/or investigator will approach patient for consent prior to surgery. Patients will be given the opportunity to review the informed consent document and ask questions about the study. The informed consent will comply with the ICH/GCP regulatory guidelines.

**Baseline:** Once consent is obtained, baseline data regarding participant characteristics, injury characteristics and PROMIS scores will be collected from the participant and entered into the electronic data collection system. Data will also be collected from the medical record regarding injury characteristics, fracture fixation, pain scores and utilization of pain alleviation modalities (pharmaceutical and nonpharmaceutical).

**Follow-up:** Participants will complete study visits at 2, 6, and 12 weeks following admission to the hospital, which may overlap with regularly scheduled standard of care clinic visits. These visits may also be completed via phone calls, text messages, or email. At these visits, participants will be asked to complete PROMIS-29 survey. Data regarding use of any pharmaceutical and nonpharmaceutical modalities for pain management will be collected at these visits. Additional variables about fracture complications will be collected from the electronic medical record.

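### Outpatient opioid use is net of unused tablets in the TENS group but comes from a prescription database in the controls, which is likely to favour TENS even with no true effect

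*Protocol*

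**What the plan says.** Protocol, Outcome Measures, Primary Outcomes: "The primary outcome will be inpatient and outpatient opioid use, defined as morphine milligram equivalents". The same paragraph continues: "Pill counts will be conducted at follow-up visits to account for unused opioids, and patients will be provided with opioid disposal kits".

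Protocol, Specific Aims, Aim 2: the alternative hypothesis is that TENS patients need less opioid, in MME, "than historical controls during hospitalization and throughout 3-month follow up".

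Protocol, Treatment Groups: controls come from an ongoing institutional study described as holding injury, patient-reported and kinematic or performance data. Opioid consumption and pill counts are not in that list. For opioids, the section points to a "database of all opioid prescriptions as well as risk factors that can be used to provide these data for the controls".

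Protocol, Study Procedures, Follow-up, which covers enrolled participants: "Data regarding use of any pharmaceutical and nonpharmaceutical modalities for pain management will be collected at these visits". On how contact is made: "These visits may also be completed via phone calls, text messages, or email".

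Protocol, Sample Size: "the primary outcome variable is morphine milligram equivalents (MME) within the first 48 hours postoperatively".

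**The concern.** A prescription database records what was ordered. A pill count shows what is left over. If leftovers are subtracted in one group and cannot be subtracted in the other, the groups are measured on different scales, and the group with the subtraction has the lower mean.

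That group is the TENS group, so the measurement difference points the same way as the Aim 2 hypothesis. A significant outpatient reduction could not be separated from this artefact. A later analysis plan could not repair it by adding data, because pill counts cannot be made afterwards for historical patients. It could only change which quantity is compared.

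**Working it through.** **1. The two groups side by side (outpatient part)**

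| | TENS group | Historical controls |
|---|---|---|
| Opioid source described | Follow-up questions and pill counts | Institutional prescription database |
| Unused tablets | Accounted for | No method described |
| Resulting quantity | Consumed MME | Prescribed MME |

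**2. The plan's own sample size.** Inputs from Sample Size: means 6.4 and 9.9 (difference 3.5), SD 5.5, two-sided 0.05, 80% power. The normal approximation gives 39 per group. The exact t calculation gives 40 (power 80.3%; 79.2% at 39). The stated 40 is reproduced, and 40/(1 − 0.20) = 50 matches the enrolment target if 20% loss is meant. The problem is one of measurement, not of a wrong number.

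**3. Expected artefact.** Assume both groups have the same true prescribing and consumption. Let *u* be the unused share of prescribed opioid and *f* the share of TENS patients with a pill count. The expected relative reduction in the TENS group is then *f* × *u*, with no treatment effect. For scale, the reduction used for planning is 3.5/9.9 = 35%, so *u* of about 35% with full counts would reproduce it by itself.

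**4. Chance of a false significant result favouring TENS.** Two-sample t-test, two-sided 0.05, counting only the TENS-favouring tail (nominal 2.5%). The standardised difference is *d* = *f* × *u*/CV, with noncentrality *d* × √(*n*/2) and 2*n* − 2 degrees of freedom.

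The protocol gives neither *u* nor the CV of outpatient MME, so both are assumed. CV 0.56 is the 48-hour planning ratio, 5.5/9.9, borrowed as one end of the range. Example: *u* = 0.20, *f* = 1, CV 0.56, *n* = 50 gives *d* = 0.20/0.556 = 0.36, noncentrality 0.36 × √25 = 1.8, and a probability of 43.0%.

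| *n* per group, *f* | *u* | CV 0.56 | CV 0.8 | CV 1.0 |
|---|---|---|---|---|
| 50, all counted | 10% | 14.3% | 9.0% | 7.1% |
| | 20% | 43.0% | 23.5% | 16.6% |
| | 30% | 76.2% | 45.9% | 31.8% |
| 50, half counted | 10% | 6.5% | 4.9% | 4.3% |
| | 20% | 14.3% | 9.0% | 7.1% |
| | 30% | 26.7% | 15.1% | 11.2% |
| 40, all counted | 10% | 12.2% | 8.0% | 6.4% |
| | 20% | 35.6% | 19.6% | 14.1% |
| | 30% | 66.5% | 38.1% | 26.3% |

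**5. Check with skewed data.** Gamma-distributed MME, TENS values multiplied by (1 − *u*), 50 per group, all counted, 40,000 simulations. At *u* = 20% the probabilities are 50.8%, 27.1% and 18.7% for CV 0.56, 0.8 and 1.0. At *u* = 30% and CV 0.56 the probability is about 88%, against 76.2% from the formula, because scaling also shrinks the TENS group's SD. In a separate run of 20,000 simulations with *u* = 0, the probability returns to about 2.5%.

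**The case against.** **The asymmetry is inferred.** The protocol does not say that leftovers are subtracted for TENS patients only, and it says the prescription database can be used for controls, not that nothing else will be. The analysis plan, which is not shown, might define outpatient MME for each group. This is why the conclusion is worded as likely. Still, the pill-count correction is written into the primary outcome, no other opioid source is named for controls, and nothing described could recover their unused tablets.

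**The direction could be offset.** Asking TENS participants about their medication may pick up opioids obtained elsewhere, which the institution's database might miss for controls. That would raise the TENS figure, and the protocol gives no means of sizing it. Remote visits may leave some TENS patients without a direct count. That shrinks the artefact and makes it uneven across patients, but does not reverse it.

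**The percentages rest on assumptions.** This stands. A more variable outcome lowers them: at *u* = 20% with full counts and 50 per group, they fall to 9.7% at CV 1.5 and 7.1% at CV 2.0. The equal-SD formula understates the effect in other settings, as the simulation shows. The ranges are therefore not bounds in either direction.

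**The powered variable is 48-hour MME.** Also true. It is largely inpatient and should be little affected by pill counts. The protocol does not describe how inpatient MME will be obtained for controls, so this concession assumes a comparable hospital source. The outpatient part nevertheless remains in the primary outcome and in Aim 2.

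**Conclusion.** The concern holds for the outpatient part of the primary outcome and should be fixed. As written, consumed MME in the TENS group is compared with prescribed MME in the controls, and the difference is likely, though not certain, to favour TENS in the absence of any effect.

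The bias in the mean is the unused share times the fraction of TENS patients counted. Over the assumed range of 10% to 30% unused and CV 0.56 to 1.0, with 50 per group, the t-test calculation turns a nominal 2.5% into 7% to 76% with full counts, or 4% to 27% with half counted. This rests on reading the pill counts as a subtraction from the TENS patients' MME, on the prescription database being the controls' only outpatient source, and on equal true prescribing and consumption. Confidence is medium, because the first two are the natural reading of the text rather than explicit statements.

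**What to change.** Amend Outcome Measures and Aim 2 as follows:

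- Every between-group opioid comparison uses the same source in both groups: inpatient MME from the medical record, and outpatient MME prescribed through 12 weeks from the institutional prescription database.
- The outpatient result is labelled prescribed MME, and the outpatient part of Aim 2 is reworded to match.
- Pill counts are kept. Pill-count-adjusted consumption is reported for the TENS group descriptively only, with the number of patients who had a direct count, and is not compared with controls.
- A limitation is stated: prescribed MME reflects prescribing, which may have changed over calendar time between the historical controls and the TENS patients.

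The practical cost is one database query for the 50 TENS patients and a protocol amendment, with no new data from patients. It assumes that inpatient records are accessible for the controls. The real cost is scientific: the outpatient comparison then measures prescribing, unblinded and against historical controls, rather than what patients took. That narrows what this part of Aim 2 can conclude, but removes a measurement difference that the comparison cannot otherwise separate from a treatment effect.

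### The 3-month opioid comparison in Aim 2 cannot be attributed to TENS alone, because only the TENS group is stated to have pill counts and opioid disposal kits

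*Protocol*

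**What the plan says.** The alternative hypothesis of Specific Aim 2 is that "Patients treated with TENS will require less opioids" (lower MME) "than historical controls during hospitalization and throughout 3-month follow up". The Outcome Measures section puts the outpatient period into the primary outcome: "The primary outcome will be inpatient and outpatient opioid use, defined as morphine milligram equivalents". The Sample Size section is narrower: "the primary outcome variable is morphine milligram equivalents (MME) within the first 48 hours postoperatively".

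For enrolled patients, Outcome Measures adds two procedures: "Pill counts will be conducted at follow-up visits to account for unused opioids, and patients will be provided with opioid disposal kits". It also provides for questions about other methods of pain relief: "Patients will also be asked about their use of nonpharmaceutical modalities at each follow-up visit or phone call, including cryotherapy, aromatherapy, and cognitive strategies". Study Procedures sets the timing of follow-up: "Participants will complete study visits at 2, 6, and 12 weeks following admission to the hospital".

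The controls are described under Overall Design, Treatment Groups and Sample Size. They are matched on injury and drawn from an institutional mobility study, which records injury details, patient-reported measures and movement data. Their opioid data are to come from a separate institutional database of prescriptions. None of these sections mentions pill counts or disposal kits for the controls, and none says when kits are given to the TENS patients.

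**The concern.** Aim 2 attributes a difference in opioid use over 3 months to the device. After discharge, however, the TENS patients differ from the controls, as described, in more than the device. Their tablets are counted and they are given a means of disposing of what is left. A patient who expects a count, or who has an easy way to discard tablets, may take fewer of them. If so, outpatient MME would fall in the TENS group with an inactive device, and the shift would favour TENS.

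This is an effect on behaviour, distinct from how opioid use is recorded. Pill counts can correct TENS use for unused tablets, while control use rests on prescriptions. That mismatch is a neighbouring problem. Measuring both groups in the same way would remove it, but would leave any behavioural effect of the procedures in place. At stake is the meaning of the outpatient half of the primary claim.

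**Working it through.** **1. The plan's own figure.** Inputs from Sample Size: means 6.4 and 9.9, SD 5.5, two-sided 0.05, power 80%.

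- Difference: 9.9 − 6.4 = 3.5; standardised, 3.5/5.5 = 0.636.
- Normal approximation: n = 2 × (1.960 + 0.842)² × 5.5²/3.5² = 2 × 7.85 × 2.469 ≈ 38.8, rounded up to 39 per group.
- Exact two-sample t-test: 39.75, rounded up to 40 per group; power at 40 is 80.3%.
- Enrolment of 50 equals 40/(1 − 0.20), an implied 20% loss.

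The stated 40 per group reproduces. All of its inputs belong to the first 48 hours. The protocol gives no mean, SD or planned difference for the outpatient period.

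**2. What each group is stated to have.**

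| | TENS group | Historical controls |
|---|---|---|
| TENS | yes | no |
| Pill counts | yes, at follow-up visits | not stated |
| Disposal kits | yes, timing not stated | not stated |
| Source of opioid data | study records, corrected by pill counts | prescription database |
| Matching | – | on injury |

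**3. What the outpatient contrast estimates.** Let T be the effect of TENS on outpatient MME and P the effect of pill counts and kits. If the controls had neither procedure, the difference between groups estimates T + P, apart from the other differences that historical controls bring. The TENS and procedure indicators are both 1 for every enrolled patient and both 0 for every control, so there is one contrast and two unknowns. Injury matching does not involve P. Covariate adjustment cannot estimate P, because the procedures do not vary within either group. An analysis plan could not repair this with these two groups.

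If all controls had the same procedures, P would cancel. If only some had them, part of P would remain. The protocol does not say which case applies.

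**4. Which window is affected.** The first follow-up visit is 2 weeks (14 days) after admission, and the 48-hour window closes 2 days after surgery. A follow-up pill count could fall inside that window only if surgery took place 14 − 2 = 12 or more days after admission, so for practical purposes the counts come later. Kits have no stated timing and would reach the 48-hour outcome only if handed out within it.

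**The case against.** The strongest reply is that nothing in the protocol says either procedure lowers opioid intake. Pill counts are introduced as measurement, and a disposal kit deals with tablets that were not taken. This stands to the extent that neither the existence nor the size of P is shown. It does not rescue the attribution, because a claim for TENS alone needs P to be zero and the design gives no means of checking that.

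A second reply is that the outcome behind the sample size is the 48-hour MME, which these procedures hardly touch. This stands and confines the point to the period after discharge. A third is that historical controls differ in many ways anyway. That is true, but this difference comes from the study's own procedures and can be dealt with by accurate wording.

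Several stronger readings are tempting and are not supported:

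- **That the controls certainly lacked these procedures.** The protocol is silent. Kits or counts may already have been routine.
- **That the controls had little research contact.** Treatment Groups calls their source study ongoing and says it collects patient-reported measures. The TENS visits may coincide with routine clinic appointments. The documents show no difference in intensity of contact.
- **That asking about cryotherapy, aromatherapy and cognitive strategies is itself a co-intervention.** Patients are asked about these methods, not offered them. This is data collection and does not carry the point.
- **That the bias can be sized against the planned 35% reduction (3.5/9.9).** That reduction belongs to the first 48 hours. Dividing an assumed outpatient effect by it mixes two windows, and the documents offer no outpatient denominator.
- **That the claim could safely run up to the first pill count.** Kits might be given at discharge, and a patient who knows a count is coming might change behaviour before it. That boundary is not clean.

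**Conclusion.** The point holds for the outpatient, 3-month part of Aim 2. As the protocol stands, a lower discharge-to-12-week MME would reflect TENS together with pill counts and disposal kits, and cannot be attributed to TENS alone. This does not mean that TENS has no part in such a difference, only that its part cannot be isolated. The likely direction of any bias favours TENS, on the assumption that the procedures reduce opioid taking rather than increase it. Its size is unknown.

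The conclusion rests on the protocol's silence about the controls and would lapse if they were shown to have had the same procedures. The 48-hour MME and the 40 per group are not called into question on this ground, unless kits are handed out within the first 48 hours.

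**What to change.** In Specific Aim 2 and in the primary-outcome paragraph of Outcome Measures:

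- Rest the superiority claim for TENS on MME in the first 48 hours after surgery, as already powered under Sample Size. This also settles the difference between the two sections over the primary outcome.
- Report discharge-to-12-week MME as an estimate for TENS plus the study's pill counts and disposal kits versus historical care, without a superiority claim for TENS alone.
- State when kits are given to enrolled patients, and whether the controls had pill counts or kits. If it is confirmed that they had the same procedures, this restriction can be lifted.

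The change is one of wording. It needs no further patients, leaves the sample size as it is and removes no study procedure. The cost is that the 3-month opioid result becomes supportive rather than confirmatory. It does not cure the separate mismatch between pill-count and prescription data, which needs its own remedy.
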